9.3.1.2. Secondary Outcomes

- Description of subtypes of AML and B-cell ALL based on the cytogenetic and molecular abnormalities, according to the WHO classification.
- Proportion of patients of each prognostic-risk group (favorable, intermediate, adverse) among newly diagnosed AML patients, based on cytogenetic profile
- Description of the treatment standard from diagnosis to inclusion of R/R ALL patients.
- Description of clinically relevant events presented by AML and relapsed/refractory B-cell ALL patients since treatment initiation until loss of follow-up or death from any cause.
- The EFS will be the measure of time since treatment initiation until failure to achieve complete remission (CR), or disease progression after CR, or death from any cause for both AML and relapsed/refractory B-cell ALL patients.
- The OS will be the measure of median time since treatment initiation until death from any cause for both AML and relapsed/refractory B-cell ALL patients.
- The OS will also assess the proportion of AML and relapsed/refractory B-cell ALL patients alive after 1, 3 and 5 years since treatment initiation.
- For AML patients who achieved CR, the RFS will be the measure of time since the CR attainment until relapse or death from any cause.
- For AML patients the response to induction and consolidation therapy will assess the proportion of patients who achieve complete remission (CR), complete remission with incomplete hematological recovery (CRI), complete remission without minimal residual disease (MDR-), partial remission (PR), and progressive disease.
- For relapsed/refractory B-cell ALL patients the response to the rescue treatment will assess the proportion of patients with complete remission (CR), complete remission without minimal residual disease (MRD-), partial remission (PR), and progressive disease.

- Heath care resource utilization description, considering the outpatient utilization, inpatient admissions, hospitalization length of stay, and concomitant medication prescription since diagnosis until the loss of follow-up or death from any cause.

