- Relapse-free survival (RFS) for newly diagnosed AML patients – considered as measured from the date of achievement of a remission until the date of relapse or death from any cause; patients not known to have relapsed or died at last follow-up are censored on the date they were last examined. Defined only for patients achieving CR, or CRI.

- Event-free survival (EFS) of newly diagnosed AML and relapsed/refractory B-cell ALL patients – considered as the measured from the date of initiation of treatment to the date of primary refractory disease, or relapse from CR, or CRi, or death from any cause; patients not known to have any of these events are censored on the date they were last examined

All computations and generation of tables, listings, graphics, and data for figures will be performed using R® version 3.5.3 or newer version (R Core Team), or a comparable statistical software package.

Medical Dictionary for Regulatory Activities Terminology (MedDRA) version 2.1 (V2.1) or newer version will be used as a standardised medical terminology. Medicinal product names will be codified using World Health Organisation Drug Dictionary (WHODrug), a dictionary maintained and updated by Uppsala Monitoring Centre (UMC).

The resource utilization (eg, number of hospital admissions, hospitalization period, procedures during hospital admissions) will be presented as mean number per patient per year (PPPY). According to the sample distribution, the data will be presented with a standard deviation (SD) or a 95% confidence interval (95% CI), which will be estimated either by Poisson regression or Gama distribution. The PPPY will be calculated as the sum of all event observed in the cohort divided by the total follow-up period (in years) of all patient in the cohort (including those who did not present the event).

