8.3.2. Outcomes

Primary outcomes

1. Description of demographic and clinical presentation characteristics at the moment of R/R B-cell ALL or AML diagnosis
2. Treatment description considering the front-line therapy and subsequent regimen(s) required for patients with R/R B-cell ALL and AML, including any systemic chemotherapy, target therapy, hematopoietic stem cell transplantation (autologous/allogenic), intrathecal chemotherapy and palliative management.

Secondary outcomes

3. Description of subtypes of AML and B-cell ALL based on the cytogenetic and molecular abnormalities, according to the WHO classification

Effective Date: 01Feb2022

4. Proportion of patients of each prognostic-risk group (favorable, intermediate, adverse) among newly diagnosed AML patients, based on cytogenetic profile
5. Description of the treatment standard from diagnosis to inclusion of R/R ALL patients
6. Description of clinically relevant events presented by AML and R/R B-cell ALL patients since treatment initiation until loss of follow-up or death from any cause;
7. The EFS will be the measure of time since diagnosis until failure to achieve complete remission (CR), or disease progression after CR, or death from any cause for both AML and R/R B-cell ALL patients;
8. The OS will be the measure of median time since diagnosis until death from any cause for both AML and R/R B-cell ALL patients;
9. The OS will also assess the proportion of AML and R/R B-cell ALL patients alive after 1, 3 and 5 years, if feasible, since treatment initiation;
10. For AML patients who achieved CR, the RFS will be the measure of time since the CR attainment until relapse or death from any cause;
11. For AML patients the response to induction and consolidation therapy will assess the proportion of patients who achieve CR, complete remission with incomplete hematological recovery (CRI), complete remission without minimal residual disease (MDR-), partial remission (PR), and progressive disease
12. For R/R B-cell ALL patients the response to the rescue treatment will access the proportion of patients with CR, complete remission without MRD-, PR, and progressive disease
13. Health care resource utilization description, considering the outpatient utilization, inpatient admissions, hospitalization length of stay, and concomitant medication prescription since diagnosis until the loss of follow-up or death from any cause.

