- Relapse-free survival (RFS) for newly diagnosed AML patients – considered as the date of achievement of a remission until the date of relapse or death from any cause; patients not known to have relapsed or died at last follow-up are censored on the date they were last examined, study enrollment, last contact, whichever comes later. Defined only for patients achieving CR, or CRI. The RFS will be measured as the treatment end date until next treatment initiation or date of death, whichever comes first, for all AML patients who achieved Complete remission/response (CR) or Complete remission/response with incomplete hematological/count recovery (CRI) at the end of treatment.
- Event-free survival (EFS) of newly diagnosed AML and R/R B-cell ALL patients – considered as the date of initiation of treatment (or date of diagnosis, if the previous is not available) to the date of primary refractory disease, or relapse from CR, or CRI, or death from any cause; patients not known to have any of these events are censored on the date they were last examined, study enrollment, last contact, whichever comes later. The EFS will be measured as the time since AML and R/R ALL initiation of treatment (or newly AML diagnosis and newly ALL diagnosis, if treatment date is not available) until i) treatment end date (or treatment start date of the next treatment line, if the previous is not available) when treatment response was Refractory disease(5) or Relapsed from CR or CRI or recurrent disease(6) as treatment response; ii) date of death, whichever comes first.
 - Clinically relevant events:
 - Hematological toxicities
 - Hepatotoxicity
 - Gastrointestinal toxicities
 - Tumor lysis syndrome
 - Fatigue
 - Dysgeusia
 - Alopecia
 - Muscle spasms
 - Infections

- Sepsis
- Secondary malignancy due to drug toxicity
- Death
- Other

Medical Dictionary for Regulatory Activities Terminology (MedDRA) version 2.1 (V2.1) or newer version will be used as a standardised medical terminology. Medicinal product names will be codified using World Health Organisation Drug Dictionary (WHODrug), a dictionary maintained and updated by Uppsala Monitoring Centre (UMC).

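### The SAP gives conflicting EFS rules on origin, events, event date and censoring, and its operational rule gives no event for non-CR responses coded partial remission, progressive disease or other

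*SAP*

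**What the plan says.** **Protocol.** Section 9.3.1.2 measures EFS "since treatment initiation until failure to achieve complete remission (CR), or disease progression after CR, or death from any cause". Section 9.7 also starts at treatment initiation but runs "to the date of primary refractory disease, or relapse from CR, or CRi, or death from any cause". Its censoring rule uses the last examination alone: "patients not known to have any of these events are censored on the date they were last examined".

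**SAP 8.3.2, item 7.** "The EFS will be the measure of time since diagnosis until failure to achieve complete remission (CR), or disease progression after CR, or death". The origin is now diagnosis.

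**SAP 8.7, EFS bullet.** The first sentence starts at treatment initiation, or at diagnosis if that date is missing, and runs "to the date of primary refractory disease, or relapse from CR, or CRI, or death from any cause". Its censoring rule takes the latest of three dates: those without "any of these events are censored on the date they were last examined, study enrollment, last contact, whichever comes later". The second sentence gives the operational rule. The event is the treatment end date, or the start of the next line if that is missing, "when treatment response was Refractory disease(5) or Relapsed from CR or CRI or recurrent disease(6) as treatment response", or death if earlier. If the treatment date is missing, the clock starts at diagnosis: "or newly AML diagnosis and newly ALL diagnosis, if treatment date is not available".

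**SAP 8.7.2, item 7.** It repeats the operational rule but censors only at last examination.

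**The concern.** Protocol 9.7 lets the SAP depart from the protocol, and EFS is not a primary endpoint, so a difference between the two documents is not in itself an error. The conflicts inside the SAP remain: 8.3.2 against 8.7 on origin and events, the first against the second sentence of the 8.7 bullet on event date, and 8.7 against item 7 on censoring. The SAP does not say which text governs, and it does not label the operational rule as a proxy.

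EFS is a named secondary objective. As written, the estimate is not reproducible. Following 8.7 also leaves some failures to reach remission uncounted and carries unobserved patients forward as event-free.

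**Working it through.** The documents state no EFS figure to reproduce, so the check is a comparison of texts, one calculation from the planned dates, and illustrations on assumed inputs.

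**1. The texts side by side**

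| Place | Origin | Non-fatal events | Event date | Censoring |
|---|---|---|---|---|
| Protocol 9.3.1.2 | treatment start | no CR; progression after CR | not stated | not stated |
| Protocol 9.7 | treatment start | primary refractory; relapse from CR/CRi | date of the event | last examined |
| SAP 8.3.2 item 7 | diagnosis | no CR; progression after CR | not stated | not stated |
| SAP 8.7, first sentence | treatment start, else diagnosis | primary refractory; relapse from CR/CRi | date of the event | latest of last examined, enrollment, last contact |
| SAP 8.7, second sentence | treatment start, else new AML or new ALL diagnosis | codes 5 and 6 | treatment end, else next-line start | not restated |
| SAP 8.7.2 item 7 | as the row above | codes 5 and 6 | as the row above | last examined |

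**2. The operational rule applied to the response list (SAP 8.7.2 items 11 and 12)**

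There are seven entries. Refractory (5) and relapsed or recurrent (6) trigger an event. Partial remission, progressive disease and other are also non-CR outcomes, but they trigger nothing until death or a later code 5 or 6. CR and CRi trigger nothing. Of the two definitions of refractory in Protocol 9.2.3, the one under treatment response requires no CR or CRi after two intensive induction courses, which is narrower than failure to achieve CR.

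**3. Relapse after CR or CRi: three branches**

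- The line stays coded CR/CRi: there is no EFS event at that relapse, although the RFS rule (8.7; 8.7.2 item 10) counts the start of the next treatment for the same patient.
- The finished line is recoded 6: the event is dated at treatment end, before the relapse.
- The relapse itself ends the line and is coded 6: the date is about right.

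The documents do not show which branch is common.

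**4. Censoring on the planned dates**

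The inputs are diagnosis from 01 January 2015 to 31 December 2019 and data collection from July 2021 to August 2022 (Protocol 4 and 6).

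- Shortest index-to-enrollment interval: 31 Dec 2019 to 1 Jul 2021 = 12 + 6 = 18 months.
- Longest: 1 Jan 2015 to 31 Aug 2022 = 7 × 12 + 8 = 92 months.

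A patient last examined at month 3 with no recorded event is censored at month 3 under item 7. Under 8.7 the same patient stays event-free to at least month 18, which adds 18 − 3 = 15 unobserved months.

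**5. Illustrations (all inputs assumed)**

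- *Uncounted PR, PD or other.* Let a share q of patients be affected, with failure at 1.5 months and a mean of m months to death or a later code 5/6. The excess in EFS at month t is q·exp(−(t − 1.5)/m). With q from 0.05 to 0.20 and m from 3 to 9, month 6 gives 0.05·e^(−1.5) = 0.011 to 0.20·e^(−0.5) = 0.121. Month 12 gives 0.05·e^(−3.5) = 0.002 to 0.20·e^(−1.167) = 0.062.
- *Censoring.* Assume a true exponential median of 9 months, so S(24) = 2^(−24/9) = 0.157. Let a fraction f be last seen uniformly over months 0 to 12, with all their later events unrecorded. Their chance of having no recorded event is (1 − 2^(−12/9))/(12·ln2/9) = 0.653. Under 8.7, 24-month EFS is about (1 − f)·0.157 + f·0.653. That is 0.21 for f = 0.1 and 0.31 for f = 0.3, against 0.16 with last examined.
- *Relapse coding.* A simulation assumed that line 1 ends at 3 months, 70% reach CR and 30–80% of non-CR patients are coded 5. Assumed medians were 10 months to relapse, 6 from relapse to death, 5 to death without CR and 60 to death in remission, with the rule applied to line 1 only. Median EFS dated at non-CR, relapse or death is about 7.1 months. Under the operational rule it is 13.3–14.5 months if no relapse is coded 6, and 3.0–6.2 months if half are coded 6 on the finished CR line. The sign of the error depends on coding practice.

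**The case against.** The strongest defence is that the 8.7 bullet states a concept and then puts it into operation with the dates available. The SAP log says 8.7 was updated after a test on 20% of the entered data, and analyses are made subject to data availability, so treatment-end and next-line dates may be all that exists. That is a fair reason to use a proxy. It does not reconcile 8.3.2 with 8.7, or 8.7 with item 7 on censoring, and it does not explain why PR and PD are not failures to achieve CR.

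A reader might infer more than the documents support:

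- *That the rule misses failures to achieve CR in general.* It does not; those coded refractory are counted.
- *That relapses are mostly missed.* Response is recorded at the end of treatment (Protocol 9.3.2), but code 6 is itself a response entry, and a relapse that ends a line can be dated about correctly.
- *That EFS outlasting RFS proves an error.* EFS starts at treatment initiation and the operational RFS at treatment end, so EFS is normally the longer time. The inconsistency is that one relapse can count for RFS and not for EFS.
- *That the R/R ALL fallback matters much.* A new ALL diagnosis date contradicts the index date in SAP 8.2.2, which is the R/R diagnosis. But inclusion requires at least one R/R treatment line and charts with excessive missing data can be excluded, so the fallback should rarely apply.
- *That enrollment carries no information.* SAP 8.7.1 describes enrolled patients as consenting, or deceased under a waiver. Enrollment with consent may show that a patient is alive; it does not show that the patient is event-free.

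**Conclusion.** The concern holds. The SAP contains incompatible EFS rules on origin, events, event date and censoring. The operational rule leaves PR, PD and other without an event until death or a later code 5 or 6. On the planned dates, 8.7 allows essentially no EFS censoring before about month 18; this is approximate because EFS starts at treatment and the protocol says dates may change.

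Uncounted PR and PD and the 8.7 censoring rule both bias EFS upward, the latter where events after the last examination go unrecorded. SAP 8.8 accepts that transfers and undocumented deaths occur. Backdated relapses bias it downward. A reader might take the illustrated shifts as the expected bias. They are not: every input except the dates is assumed, and net size and direction cannot be estimated from the documents. Any single CR share would also misdescribe one cohort, since Protocol 7.3 cites about 40% complete response after first salvage in ALL. The CRF code list and the TLF workbook were not available and could map PR or PD to an event; the SAP text does not. EFS is secondary and descriptive, so the harm is to the estimate and its reproducibility, not to a test.

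**What to change.** State one EFS definition in SAP 8.3.2, 8.7 and 8.7.2 item 7, and say that it supersedes Protocol 9.3.1.2 and 9.7.

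- **Origin:** treatment initiation; if missing, the index-date diagnosis (the R/R diagnosis for B-cell ALL).
- **Events:** (i) failure to achieve CR or CRi on initial treatment (AML) or first rescue treatment (R/R ALL), counting PR and PD as final response as well as refractory, dated at response assessment or, if not collected, at the end of that course as a flagged proxy; (ii) relapse or progression after CR/CRi, dated at documented relapse or, if not collected, at next-line start flagged as a proxy, and not at the end of the course in which CR was recorded; (iii) death.
- **Censoring:** date last examined in both sections, as already in Protocol 9.7 and item 7.
- **Labels:** correct the R/R-event row label in item 7, which omits death. The similar label in item 8 concerns OS and should be handled separately.

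Optional: a rule for responses coded other, and the codes 5/6 rule kept as a sensitivity analysis.

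The cost is SAP wording and minor reprogramming. No protocol amendment is needed for a secondary outcome. The downsides should be stated in the SAP. The documents do not confirm that relapse or response-assessment dates are collected, so some dates will be proxies. Patients are censored earlier. Deaths learned of after the last examination still count, while later known-alive time of survivors is dropped.

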9.3.2. Variables and Epidemiological Measurements

The information will be extracted only if available in the medical chart. No assumptions or interpretation should be done in order to describe the parameter of interest. The following variables will be collected:

- **Patient demographics:** age at diagnosis, gender at birth, country of residence.
- **Medical history:** comorbidities, family history, prior exposure to toxic agents, prior malignancy, therapy for prior malignancy, information on smoking, history of bleeding episodes.
- **Clinical information at diagnosis:** age at diagnosis, performance status (Karnofsky performance status [KPS] or Eastern Cooperative Oncologic Group [ECOG]).
- **Diagnosis information:** hematological parameters (total blood count, differential count, hemoglobin level), bone marrow aspirate/biopsy, cytogenetics, screening for gene mutations and rearrangements, immunophenotyping assessment.
- **Treatment information:** all treatment regimens used since diagnosis until loss of follow-up or death. It will include front-line induction therapies, consolidation therapies, rescue therapies, conditioning therapy, hematological stem cell transplantation (autologous/allogenic), intrathecal chemotherapy, palliative care.
- **Clinically relevant events:**
 - Hematological toxicities described as: febrile neutropenia, anemia/thrombocytopenia that requires blood transfusion, bleeding events.
 - Hematological stem cell transplantation (autologous/allogenic) and transplant complications such as graft-versus-host disease (GvHD), stem cell (graft) failure.
 - Gastrointestinal toxicities: oral mucositis, nausea, vomiting, diarrhea.
 - Hepatotoxicity: hepatic enzymes elevation, jaundice, ascites, abdominal pain.
 - Other events: tumor lysis syndrome, fatigue, dysgeusia, alopecia, muscle spasm, Infections and sepsis.
 - Secondary malignancy or central nervous system (CNS) involvement.
 - Any serious adverse even.t
- **Patient response at the end of treatment:**
 - Patient response according to International Working Group (IWG) criteria.⁶⁹
 - Methodology for the assessment of minimal residual disease.

PFIZER CONFIDENTIAL

- **Cytogenetic risk:**
 - Favorable, intermediate, adverse for AML.
 - Good, intermediate, poor, undetermined for B-cell ALL.

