- Time to next treatment;
- Total number of cycles;
- Patients that withdraw and reasons for withdrawing
- Dose reduction
- CNS involvement at disease progression
- Radiotherapy
 - Duration, dose, and local of application
- Intrathecal chemotherapy
 - Drug administered intrathecally
- Stem cell transplant (SCT)
 - Laboratory exams for SCT
 - Post-transplant event
- Laboratory exams before and after treatment line

R/R B-cell ALL patients:

- Regimen type
- Drug regimen prescribed
- Treatment duration
- Time to next treatment
- Total number of cycles
- Patients that withdraw and reasons for withdrawing
- CNS involvement at disease progression
- Radiotherapy
 - Duration, dose, and local of application
- Intrathecal chemotherapy
 - Drug administered intrathecally
- Stem cell transplant (SCT)
 - Laboratory exams for SCT
 - Post-transplant event
- Laboratory exams before and after treatment line

Secondary Objective(s)

3. For each treatment line, only descriptive data (absolute number, frequency, mean ± standard deviation, median, interquartile range, minimum or maximum) will be described for cytogenetic and/or molecular testing and immunophenotyping for each newly AML and R/R B-cell ALL patients cohorts:

newly AML and R/R AML

- Molecular test performed
- AML translocation result
- Molecular profile;
- AML WHO classification
 - AML with recurrent genetic abnormalities
 - AML with t(8;21)(q22;q22.1);RUNX1-RUNX1T1
 - AML with inv(16)(p13.1q22) or t(16;16)(p13.1;q22);CBFB-MYH11

- APL with PML-RARA
- AML with t(9;11)(p21.3;q23.3);MLLT3-KMT2A
- AML with t(6;9)(p23;q34.1);DEK-NUP214
- AML with inv(3)(q21.3q26.2) or t(3;3)(q21.3;q26.2); GATA2, MECOM
- AML (megakaryoblastic) with t(1;22)(p13.3;q13.3);RBM15-MKL1
- Provisional entity: AML with BCR-ABL1
- AML with mutated NPM1
- AML with biallelic mutations of CEBPA
- Provisional entity: AML with mutated RUNX1
- AML with myelodysplasia-related changes
- Therapy-related myeloid neoplasms
- AML, NOS
- Immunophenotyping result

newly B-cell ALL and R/R B-cell ALL

- Molecular test performed
- Molecular profile;
- ALL cytogenetic risk classification according to WHO for B-lymphoblastic leukemia/lymphoma
 - B-lymphoblastic leukemia/lymphoma, NOS
 - B-lymphoblastic leukemia/lymphoma with recurrent genetic abnormalities
 - B-lymphoblastic leukemia/lymphoma with t(9;22)(q34.1;q11.2);BCR-ABL1
 - B-lymphoblastic leukemia/lymphoma with t(v;11q23.3);KMT2A rearranged

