 - B-lymphoblastic leukemia/lymphoma with t(12;21)(p13.2;q22.1); ETV6-RUNX1
 - B-lymphoblastic leukemia/lymphoma with hyperdiploidy
 - B-lymphoblastic leukemia/lymphoma with hypodiploidy
 - B-lymphoblastic leukemia/lymphoma with t(5;14)(q31.1;q32.3) IL3-IGH
 - B-lymphoblastic leukemia/lymphoma with t(1;19)(q23;p13.3);TCF3-PBX1
 - Provisional entity: B-lymphoblastic leukemia/lymphoma, BCR-ABL1-like
 - Provisional entity: B-lymphoblastic leukemia/lymphoma with iAMP21
- Immunophenotyping result

4. For each cytogenetic and/or molecular testing for newly AML, the risk stratification will be described with frequencies and absolute percentages for each treatment line:

newly AML and R/R AML

- AML cytogenetic risk classification according to 2017 European LeukemiaNet (ELN)
 - Favorable
 - Intermediate
 - Poor/Adverse

R/R B-cell ALL

- ALL cytogenetic risk classification
 - Good prognosis
 - Intermediate prognosis
 - Poor prognosis
 - Undetermined prognosis

5. Data from previous treatment lines from diagnose until study inclusion will be described for newly B-cell ALL patients and R/R B-cell ALL patients. For each treatment line, no statistical testing will be carried out. Only descriptive data will be reported (absolute number, frequency, mean ± standard deviation, median, interquartile range, minimum or maximum) for:

Newly B-cell ALL patients (treatment lines from ALL diagnose until study inclusion)

- ALL cytogenetic risk classification
- Regimen type.
- Drug regimen prescribed
- Treatment duration
- Time to next treatment
- Total number of cycles
- Number of patients with dose reduction;
- Number of patients with regimen withdraw;
 - Reasons of regimen withdraw;
- Radiotherapy
 - Duration, dose, and local of application
- Intrathecal chemotherapy
 - Drug administered intrathecally
- Stem cell transplant (SCT)

6. Clinically relevant events of newly AML and R/R B-cell ALL patients will be describe by treatment line and data will be reported as absolute number, frequency, mean ± standard deviation, median, interquartile range, minimum or maximum for:

newly AML

- Period of start of the event from start of first-line treatment;
- Clinical event description;
 - Hematological toxicities;
 - Gastrointestinal toxicities;
 - Hepatotoxicity.
- Most common adverse events description

R/R B-cell ALL

- Period of start of the event from start of first-line treatment;
- Clinical event description;
 - Hematological toxicities;
 - Gastrointestinal toxicities;

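### SAP 8.7 limits secondary malignancy to drug-caused cases where the protocol sets no such limit, and the event output in item 6 does not match the event list

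*SAP*

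**What the plan says.** Protocol 9.3.2 defines the clinically relevant events. Besides haematological, gastrointestinal and hepatic toxicity, it lists:

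- transplantation and "transplant complications such as graft-versus-host disease (GvHD), stem cell (graft) failure";
- "Other events: tumor lysis syndrome, fatigue, dysgeusia, alopecia, muscle spasm, Infections and sepsis";
- "Secondary malignancy or central nervous system (CNS) involvement";
- "Any serious adverse even.t" (a misprint for event).

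The same section tells abstractors: "No assumptions or interpretation should be done in order to describe the parameter of interest".

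SAP 8.7 has its own list of 13 entries. It keeps the toxicity classes, tumour lysis, infections, sepsis and the minor events, and adds death and a residual category. For second malignancies it reads "Secondary malignancy due to drug toxicity". CNS involvement, transplant complications and serious adverse events are not on the list.

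The output for this objective is item 6 of SAP 8.7.2. It opens: "Clinically relevant events of newly AML and R/R B-cell ALL patients will be describe by treatment line". For each cohort it then names haematological, gastrointestinal and hepatic toxicity, and adds a description of the commonest adverse events. Item 2, on treatment patterns, separately plans "CNS involvement at disease progression" and a post-transplant event output, both for AML and for R/R B-cell ALL.

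**The concern.** The SAP repeats the protocol's objective and its outcome 6 without change, yet defines one component more narrowly and gives no reason. A causal qualifier on a second malignancy changes what is counted. A case after radiotherapy or transplant, both of which item 2 records as treatments, or a case with no cause in the chart, does not fit the row. A reader of the final report would take the row as the frequency of second malignancy when it is only the frequency of second malignancy with a charted drug cause.

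The same drift affects CNS involvement, which the SAP limits in time, and serious adverse events, which lose their place altogether. The list in 8.7 and the output in item 6 then disagree with each other, so two programmers could produce different event tables from the same SAP.

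**Working it through.** The documents give no event count or rate on this point, so the check is a comparison of lists.

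| Protocol 9.3.2 class | SAP 8.7 list | SAP 8.7.2 output |
|---|---|---|
| Haematological toxicity | named | item 6, named |
| Gastrointestinal toxicity | named | item 6, named |
| Hepatotoxicity | named | item 6, named |
| Tumour lysis | named | no own line |
| Fatigue | named | no own line |
| Dysgeusia | named | no own line |
| Alopecia | named | no own line |
| Muscle spasm | named | no own line |
| Infections | named | no own line |
| Sepsis | named | no own line |
| Secondary malignancy | narrowed to drug-caused | no own line |
| Transplant complications | absent | item 2, post-transplant event |
| CNS involvement | absent | item 2, at progression only |
| Any serious adverse event | absent | none named |

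**Protocol against SAP 8.7.** Of 14 classes, 10 are named, 1 is narrowed and 3 are absent (10 + 1 + 3 = 14). Of the 3 absent, transplant complications have an output elsewhere, CNS involvement has a narrower one, and serious adverse events have none.

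**SAP 8.7 against item 6.** The 13 SAP entries are the 11 named or narrowed above plus death and the residual category. Item 6 names 3 of 13 (23%), leaving 10. Death is the overall survival event and is reported there, and the residual category is not a class of its own. That leaves 8 classes whose tabulation rests on item 6's opening sentence and on the summary of the commonest adverse events, for which no threshold or number of events is given.

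**Effect of the qualifier.** Let N be the second malignancies in the charts and a the share with a drug cause written down. Abstractors may not interpret, so the row shows a × N and (1 − a) × N leaves it. The documents give neither N nor a. The loss from the row therefore runs from none (a = 1) to all (a = 0), and nothing in the plan narrows that range.

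**CNS timing.** Outcome 6 in SAP 8.3.2 runs from treatment initiation to loss of follow-up or death. An output at disease progression covers only part of that window.

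**Serious events.** The reporting duty in SAP section 10 covers events explicitly attributed to the sponsor's drugs and exposure scenarios for its products. It does not supply a study table of serious events.

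**The case against.** Four counter-arguments deserve weight.

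- *The SAP may modify the plan.* Protocol 9.7 allows this and requires an amendment only for major changes to primary endpoints. That stands as a matter of procedure. But the objective and outcome are carried over unchanged and no narrowing is declared, so the two texts still conflict.
- *The residual category catches the rest.* It can, so it is wrong to say that unattributed second malignancies are lost from the data. But a case reported there is not reported as a second malignancy, and item 6 has no residual line.
- *Copying a charted attribution is not interpretation.* This is correct; the qualifier need not breach the abstraction rule. It does make the row depend on whether the treating physician wrote down a cause.
- *The table shells are not visible.* SAP 13.1 points to a spreadsheet whose contents are not in the text. It may hold more rows than item 6, so no claim that a table is missing can be made.

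A reader might infer that infection, sepsis, tumour lysis and transplant complications are undercounted or left untabulated. The documents do not support that. The first three are named in SAP 8.7, item 6's opening sentence covers clinically relevant events as a whole, and transplant events have an output in item 2 for both cohorts. What can be said is that item 6 gives 8 listed classes no line of their own, and that a summary of the commonest events may pass over rare severe ones.

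**Conclusion.** The point holds in a limited form. The clear conflict is the secondary malignancy line: the SAP's stated rule is narrower than the protocol's and, applied as written, understates that event in its named row. Alongside it are three alignment gaps: CNS involvement is limited to progression, serious adverse events have no named output, and item 6 does not mirror the list in 8.7.

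The countable size is 1 of 14 protocol classes narrowed and 3 absent from the SAP list, of which 1 has an output elsewhere, 1 a narrower output and 1 none; and 3 of 13 SAP entries named in item 6. A reader may want a percentage for second malignancies missed, but any such figure would only restate an assumed share with a charted drug cause.

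The consequence is confined to one descriptive secondary objective with no hypothesis test. The primary and survival outcomes are untouched. The conclusion assumes that the table shells follow the SAP text.

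**What to change.** In SAP 8.7:

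- change the line to *Secondary malignancy (any cause)*, with charted attribution as a separate column if wanted;
- add CNS involvement at any time and any serious adverse event to the list;
- cross-refer transplant complications to the post-transplant event output in item 2.

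In SAP 8.7.2 item 6, tabulate every class on the list for both cohorts and keep the commonest adverse events as an extra table. Align the table shells in 13.1.

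The cost is SAP wording and additional table rows, since protocol 9.3.2 already requires these data. One caveat: the eCRF is not in the reviewed documents. If its category carries the same drug-toxicity qualifier, rewording the SAP will not recover unattributed cases, and the report should state that limitation.
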